8.2 SAFETY ENDPOINTS

Variable	Role	Operational definition
Major bleeding event ¹ after index date	Outcome (primary endpoint)	Major bleeding after index date will be identified using hospital claims which had a bleeding diagnosis code as the first listed ICD-10 or disease code (Appendix, Table 7). An event occurrence of major bleeding is defined as a case that "21: Disease name behind hospitalization" in DPC database. Time-to-major bleeding will be defined as the number of days from the index date to the occurrence of the first major bleeding event.
Any bleeding event ² after index date	Outcome (secondary endpoint)	Any bleeding after index date will be identified using hospital claims which had a bleeding diagnosis code as the first listed ICD-10 or disease code (Appendix, Table 7). Time-to-any bleeding will be defined as the number of days from the index date to the occurrence of the first any bleeding event.
Major GI bleeding event after index date	Outcome (secondary endpoint)	Major GI bleeding after index date will be identified using hospital claims which had a GI bleeding diagnosis code as the first listed ICD-10 or disease code (Appendix, Table 8). An event occurrence of major bleeding is defined as a case that "21: Disease name behind hospitalization" in DPC database. Time-to-major GI bleeding will be defined as the number of days from the index date to the occurrence of the first major GI bleeding event.
Any GI bleeding event after index date	Outcome (secondary endpoint)	Any GI bleeding after index date will be identified using hospital claims which had a GI bleeding diagnosis code as the first listed ICD-10 or disease code (Appendix-). Time-to-any GI bleeding will be defined as the number of days from the index date to the occurrence of the first any GI bleeding event.

Major intracranial hemorrhage event after index date	Outcome (secondary endpoint)	Intracranial hemorrhage after index date will be identified using hospital claims which had an intracranial hemorrhage diagnosis code as the first listed ICD-10 or disease code (Appendix-2). Time to major intracranial hemorrhage will be defined as the number of days from the index date to the occurrence of the first intracranial hemorrhage event.
Any intracranial hemorrhage event after index date	Outcome (secondary endpoint)	Intracranial hemorrhage after index date will be identified using hospital claims which had an intracranial hemorrhage diagnosis code as the first listed ICD-10 or disease code (Appendix-2). Time to any intracranial hemorrhage will be defined as the number of days from the index date to the occurrence of the first intracranial hemorrhage event.

^{1,2} Any bleeding will be defined based on definitions listed in Appendix-3. Among any bleeding events, bleeding events that requires hospitalization will be defined as “major bleeding”.

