3 STUDY DESIGN

This is a retrospective observational study using data from the MDV database (data set from March 1st, 2011 to December 31st, 2017). Among patients registered in the database patients are selected based on the inclusion and exclusion criteria (see below). The first observed prescription of apixaban, dabigatran, edoxaban, rivaroxaban or warfarin is used to identify the patient's index date (date of the first prescription of any OACs is defined as "index date") and treatment cohort. Study measures include: (1) for safety evaluation: major bleeding and any bleeding; (2) for effectiveness evaluation: a composite of ischemic stroke, hemorrhagic stroke or SE. The follow-up period is variable, and will begin on the next day of the index date and continue until the earliest of the following scenarios – occurrence of target outcome event (details available in Section 8.2); discontinuation of the index OAC; switching from the index OAC; withdrawal from the database.

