6.2 STATISTICAL DECISION RULES

All statistical tests will be performed at $p=0.05$ (two-sided) with no adjustment for multiplicity.

Based on results of Japanese sub-population in confirmatory trials for NOACs, the required sample size to detect a significant difference in stroke/SE was calculated. The following sample size calculation is based on the significance level of 0.05 (two-sided) and power of 80%.

Desired Power	Hazard Ratio	Event Rate (Control)	Required Sample Size per Group
0.8	0.6	1.2 %/year	3,166
		1.6 %/year	2,378
		2.1 %/year	1,815
		2.6 %/year	1,469

Desired Power	Hazard Ratio	Event Rate (Control)	Required Sample Size per Group
	0.7	1.2 %/year	6,083
		1.6 %/year	4,570
		2.1 %/year	3,488
		2.6 %/year	2,823
	0.8	1.2 %/year	14,683
		1.6 %/year	11,031
		2.1 %/year	8,422
		2.6 %/year	6,817

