8 ENDPOINTS AND COVARIATES

8.1 EFFICACY/ EFFECTIVENESS ENDPOINT(S)

Variable	Role	Operational definition
Stroke/SE (composite) event after index date	Outcome (primary endpoint)	Operational definition of Stroke and SE will follow the operational definition of Stroke event after index date and SE event after index date. Time to events will be defined as the number of days from the index date to the occurrence of the first stroke or SE.
Ischemic stroke event after index date	Outcome (secondary endpoint)	Ischemic stroke after index date not including the index date will be identified using hospital claims which had an ischemic stroke diagnosis code as the first listed ICD-10 diagnosis code (Appendix, Table 5). An event occurrence of ischemic stroke is defined as a case that "01: Disease name which input the most medical resources", "02:Sub-disease name", "11: Main disease name", "21: Disease name behind hospitalization", or "31: Disease name which input the second most medical resources" in DPC database. Time to ischemic stroke will be defined as the number of days from the index date to the occurrence of the first ischemic stroke.
Hemorrhagic stroke event after index date	Outcome (secondary endpoint)	Hemorrhagic stroke after index date not including the index date will be identified using hospital claims which had a hemorrhagic stroke diagnosis code as the first listed ICD-10 diagnosis code (Appendix, Table 5). An event occurrence of hemorrhagic stroke is defined as a case that "01: Disease name which input the most medical resources", "02:Sub-disease name", "11: Main disease name", "21: Disease name behind hospitalization", or "31: Disease name which input the second most medical resources" in DPC database. Time to hemorrhagic stroke will be defined as the number of days from the index date to the occurrence of the first hemorrhagic stroke.
SE event after index date	Outcome (secondary endpoint)	SE after index date not including the index date will be identified using hospital claims which had a SE diagnosis code as the first listed ICD-10 diagnosis code (Appendix, Table 5). An event occurrence of SE is defined as a case that "01: Disease name which input the most medical resources", "02:Sub-disease name",

Variable	Role	Operational definition

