8.4 COVARIATES

We will use demographic and clinical information available at the index date and baseline period of the initiation prescription for apixaban, edoxaban, and warfarin cohorts.

Variable	Role	Operational definition
Sex Category	Baseline characteristic	Dichotomous variable equals 1 if sex is male and 2 if female
Age	Baseline characteristic	Age (in years) at the index date
Physician specialty	Baseline characteristic	Dichotomous variable equals 1 if a physician specialty on the index date is categorized into a cardiac specialty and 0 if others. Following specialties will be categorized as the cardiac specialty: cardiology stroke, cardiovascular surgery, pediatric cardiology, neurosurgery, cardiovascular medicine, and neurology. If there are ≥ 1 specialties but including the cardiac specialty, the physician specialty will be regarded as the cardiac specialty.
Hospital size (<500 beds or not)	Baseline characteristic	Dichotomous variable equals 1 if hospital size on the index date is <500 beds and 0 if ≥ 500 beds.
Hospitalization status on index date	Baseline characteristic	Dichotomous variable equals 1 if hospitalization status is inpatient and 0 if outpatient.
CHADS ₂	Baseline characteristic	CHADS ₂ score will be calculated based on age and the presence of congestive heart failure, hypertension, diabetes, and stroke or TIA.

CHA ₂ DS ₂ -VASC	Baseline characteristic	CHA ₂ DS ₂ -VASC score will be calculated based on age and the presence of congestive heart failure, hypertension, diabetes, stroke or TIA, vascular disease and sex category.
PT-INR (Prothrombin time-international normalized ratio)	Baseline period	Continuous variable. * Only available for patients treated with warfarin
Heart failure diagnosis in baseline	Baseline characteristic	Dichotomous variable equals 1 if there are ≥ 1 diagnoses for heart failure ICD-10 or disease codes during the baseline period.
Coronary heart disease diagnosis in baseline	Baseline characteristic	Dichotomous variable equals 1 if there are ≥ 1 diagnoses for coronary heart disease ICD-10 or disease codes during the baseline period.
Peripheral arterial disorder diagnosis in baseline	Baseline characteristic	Dichotomous variable equals 1 if there are ≥ 1 diagnoses for peripheral arterial disorder ICD-10 or disease codes during the baseline period.

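### A brain bleed arising in hospital can be a primary stroke/SE event and a major intracranial hemorrhage, yet not a primary major bleeding event

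*SAP*

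**What the plan says.** **Major bleeding (primary safety, SAP 8.2).** The code must be first listed and must appear in DPC field "21: Disease name behind hospitalization". Major GI bleeding has the same condition. The footnote to 8.2 puts the idea in words: "Among any bleeding events, bleeding events that requires hospitalization will be defined as" major bleeding.

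**Hemorrhagic stroke (part of primary stroke/SE, SAP 8.1).** The code must also be first listed, but any of five fields is enough: 01, 02, 11, 21 or "31: Disease name which input the second most medical resources".

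**Major intracranial hemorrhage (secondary, SAP 8.2).** No DPC field is named. Apart from its label, the row reads the same as the one for any intracranial hemorrhage.

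**Time at risk (SAP 3 and 10.1.3; protocol 7.2).** Follow-up "will begin on the next day of the index date and continue until the earliest of the following scenarios", namely the event, discontinuation, switching or withdrawal; SAP 10.1.3 adds the end of the intended two-year period. Rates use all patient-years at risk. No text removes inpatient days or moves the start to discharge.

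**Inpatient starters.** They are in the cohort, because SAP 8.4 records hospitalization status on the index date: "Dichotomous variable equals 1 if hospitalization status is inpatient and 0 if outpatient". That variable is not in the propensity score list of SAP 10.1.1.

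**The concern.** The reason for an admission is fixed when the admission begins. A bleed that starts later in the same stay would ordinarily be coded elsewhere, so it would miss the field-21 condition. For patients who start treatment in hospital, the first days on drug fall in such a stay.

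Two things are at stake. First, the primary safety and primary effectiveness endpoints can classify the same brain bleed differently. The SAP's own major intracranial hemorrhage endpoint also stops being a subset of major bleeding, which conflicts with the footnote's rule that hospitalization separates major from other bleeding. Second, if inpatient starts or lengths of stay differ between warfarin and a NOAC, the early undercount of major bleeds differs by arm.

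**Working it through.** **1. The plan's own figure.** The only sample size in the documents is for stroke/SE: SAP 6.2 says "the required sample size to detect a significant difference in stroke/SE was calculated". For HR 0.6, a control rate of 1.2%/year, two-sided 0.05 and 80% power, the Schoenfeld events are 4(1.960 + 0.842)² / (ln 0.6)² ≈ 120.3. With two years of follow-up and no dropout, p1 = 1 − exp(−0.024) = 0.0237 and p2 = 1 − exp(−0.0144) = 0.0143. N per group = 120.3 / 0.0380, which with unrounded inputs rounds up to 3,166, the stated value. The other eleven cells agree to within about 1.2% (the largest gap is 6,898 computed against 6,817 stated). This table is unaffected. No calculation is given for major bleeding.

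**2. One event through each definition.** Take a first-listed I61 bleed that arises during a stay and is coded in field 01, 02, 11 or 31.

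| Endpoint | Condition | Counted? |
|---|---|---|
| Stroke/SE (primary) | I60–I62 (with one exclusion under I62), any of five fields | Yes |
| Major intracranial hemorrhage (secondary) | Appendix-5 code, no field named | Yes |
| Any bleeding | Appendix-3 code, no field named | Yes |
| Major bleeding (primary) | Appendix-3 code, field 21 only | No |

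The code lists largely overlap. Appendix-4 takes I60 and I61 whole, and I62 without nontraumatic extradural haemorrhage. Appendix-3 and Appendix-5 itemise these groups, although both go from I611 straight to I613.

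**3. Illustrative size.** None of the following inputs is in the documents. Assume a constant hazard, a true HR of 1, a share p of inpatient starters, L days of index stay left after starting, mean follow-up of F days, and no countable major bleed of any kind during that stay. The last assumption makes this the full effect of the field-21 rule over the index stay, for intracranial and all other bleeds together. The observed rate is the true rate times (F − pL)/F, so the NOAC/warfarin ratio is (F − p_N·L)/(F − p_W·L).

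- Equal shares (50% and 50%) and equal stays: the ratio is 1.00. The rate in each arm is understated by 0.5% (L = 7, F = 730: 3.5/730) to 5.8% (L = 21, F = 180: 10.5/180).
- 60% on warfarin, 30% on NOAC, full follow-up: from (730 − 2.1)/(730 − 4.2) = 1.003 to (180 − 6.3)/(180 − 12.6) = 1.038.
- The same shares, first 30 days only: from (30 − 2.1)/(30 − 4.2) = 1.08 (L = 7) to (30 − 6.3)/(30 − 12.6) = 1.36 (L = 21).
- Inpatient starters only, with unequal stays: 7 days against 14 over 365 gives 358/351 = 1.020; 10 days against 21 over 180 gives 170/159 = 1.069. If the 45% inpatient share of the database (SAP 4.1) is borrowed for both arms, these become (365 − 3.15)/(365 − 6.30) = 1.009 and (180 − 4.50)/(180 − 9.45) = 1.029. That 45% is not a share of OAC starters.

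A ratio above 1 means that warfarin bleeds are undercounted more. If NOAC starters are more often inpatients or stay longer, the ratios invert (1/1.038 = 0.963).

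**The case against.** **The definition is a declared choice.** The footnote and field 21 agree that major bleeding means bleeding that leads to hospitalization. Stroke/SE is a different endpoint, and disagreement on one patient is not in itself a contradiction. In-hospital bleeds are not lost either: any bleeding has no field condition, and SAP 10.1.8 lists it as primary safety (8.2 calls it secondary). This stands for bleeding in general. It does not explain why an event that the SAP itself calls a major intracranial hemorrhage need not be a major bleed.

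**The effect is small and unsigned.** This stands for full follow-up.

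**Stronger readings that the documents do not support.** A reader might infer that inpatient starters cannot have the primary safety event until discharge. The SAP does not say how events are dated, how bleeds arising in hospital are coded, or whether field 21 of the index admission itself is excluded. The major bleeding row also lacks the explicit exclusion of the index date found in the stroke and SE rows of 8.1, and a transfer might open a new admission. A reader might also take 1.02 to 1.07 as the bias in the trial's HR. That range rests on assumed stays and applies to inpatient starters only.

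**Delayed entry is not a clean remedy.** Starting the major-bleeding clock at discharge would discard index-stay brain bleeds, so the mismatch with stroke/SE would remain. It would condition on reaching discharge on the index drug and in the database, let matched partners enter at different times, and leave later stays untouched. This objection stands in full and rules out delayed entry as the primary rule.

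**Conclusion.** The definitions do not fit together. On the wording of SAP 8.1 and 8.2, an intracranial bleed arising in hospital can count towards primary stroke/SE and major intracranial hemorrhage but not towards primary major bleeding, while the days on which it arises count as time at risk. This conclusion needs no assumed numbers, only that such a bleed is first listed and coded in field 01, 02, 11 or 31.

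The effect on the major-bleeding hazard ratio cannot be sized from the documents, which give neither the inpatient share nor the length of stay by drug. Under the assumptions above it is about 1.00 to 1.04 over full follow-up, larger in the first month, and of either sign. The early part of the Kaplan-Meier curves and, to a lesser extent, the one-year sensitivity analysis are more exposed than the two-year HR. Nothing in the plan balances inpatient start directly: it is not a propensity score covariate, and the Cox adjustment in SAP 10.1.3 is triggered only by imbalance in propensity score components. Baseline heparin is at best a partial proxy. The point should be corrected because it changes which events the primary safety endpoint counts, not because a large bias has been shown.

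**What to change.** - In SAP 8.2, count as major bleeding every event accepted as hemorrhagic stroke under 8.1, in addition to bleeds in field 21. Start from the day after the index date, with time zero unchanged.
- Redefine major intracranial hemorrhage to match: an Appendix-5 intracranial code in field 21, or a hemorrhagic stroke accepted under 8.1. It is then a subset of major bleeding and differs from any intracranial hemorrhage. Check that every code under I60–I62 accepted in Appendix-4 is also in Appendix-3 and Appendix-5.
- Keep the field-21-only rule as a sensitivity analysis.
- Use delayed entry at discharge from the index stay only as a sensitivity analysis of the field-21-only definition, for major and major GI bleeding.
- Bring the major bleeding entry in protocol Table 1, which names no DPC field, into line with SAP 8.2.

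**Cost.** SAP wording, a code change, an entry-time variable for the sensitivity analysis, and some loss of comparability with the sponsor's earlier study. Protocol 7.7 says that major changes to primary endpoint definitions or their analyses would be reflected in an amendment, so one may be needed. GI and other bleeds would still depend on field 21, so those arising in hospital would continue to be counted only under any bleeding or any GI bleeding. The report should state this.

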Treated with gastric secretion inhibitor in baseline	Baseline period	Dichotomous variable equals 1 if there are ≥ 1 prescriptions of gastric secretion inhibitor drug ATC or receipt codes during the baseline period.
Treated with statin-based drug in baseline	Baseline period	Dichotomous variable equals 1 if there are ≥ 1 prescriptions of statin-based drug ATC or receipt codes during the baseline period.
Treated with anti-hypertensives in baseline	Baseline period	Dichotomous variable equals 1 if there are ≥ 1 prescriptions of anti-hypertensive ATC or receipt codes during the baseline period.
Treated with anti-arrhythmics in baseline	Baseline period	Dichotomous variable equals 1 if there are ≥ 1 prescriptions of anti-arrhythmics ATC or receipt codes during the baseline period.
Treated with beta-blockers in baseline	Baseline period	Dichotomous variable equals 1 if there are ≥ 1 prescriptions of beta-blockers ATC or receipt codes during the baseline period.
Treated with heparins in baseline	Baseline period	Dichotomous variable equals 1 if there are ≥ 1 prescriptions of heparins ATC or receipt codes during the baseline period.
Cardioversion in baseline	Baseline period	Dichotomous variable equals 1 if there is ≥ 1 operation of cardioversion receipt codes during the baseline period.
Major bleeding in follow-up	Follow-up period	Dichotomous variable equals 1 if there are ≥ 1 diagnoses for major bleeding ICD-10 or disease codes during the follow-up period.
Any bleeding in follow-up	Follow-up period	Dichotomous variable equals 1 if there are ≥ 1 diagnoses for any bleeding ICD-10 or disease codes during the follow-up period.
Stroke/SE in follow-up	Follow-up period	Dichotomous variable equals 1 if there are ≥ 1 diagnoses for stroke or SE ICD-10 or disease codes during the follow-up period.

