Myocardial infarction diagnosis in baseline	Baseline characteristic	Dichotomous variable equals 1 if there are ≥ 1 diagnoses for myocardial infarction ICD-10 or disease codes during the baseline period.
Hyperthyroidism or thyrotoxicosis in baseline	Baseline characteristic	Dichotomous variable equals 1 if there are ≥ 1 diagnoses for hyperthyroidism ICD-10 or disease codes during the baseline period.
Stroke, TIA or SE diagnosis in baseline	Baseline characteristic	Dichotomous variable equals 1 if there are ≥ 1 diagnoses for Stroke, TIA or systemic embolism ICD-10 or disease codes during the baseline period.
Renal dysfunction diagnosis in baseline	Baseline characteristic	Dichotomous variable equals 1 if there are ≥ 1 diagnoses for renal dysfunction ICD-10 or disease codes during the baseline period.
Liver dysfunction diagnosis in baseline	Baseline characteristic	Dichotomous variable equals 1 if there are ≥ 1 diagnoses for liver dysfunction ICD-10 or disease codes during the baseline period.
Bleeding diagnosis in baseline	Baseline characteristic	Dichotomous variable equals 1 if there are ≥ 1 diagnoses for bleeding ICD-10 or disease codes during the baseline period.
Hypertension diagnosis in baseline	Baseline characteristic	Dichotomous variable equals 1 if there are ≥ 1 diagnoses for hyper tension ICD-10 or disease codes during the baseline period.
Diabetes mellitus diagnosis in baseline	Baseline characteristic	Dichotomous variable equals 1 if there are ≥ 1 diagnoses for diabetes mellitus ICD-10 or disease codes during the baseline period.
Cancer diagnosis in baseline	Baseline period	Dichotomous variable equals 1 if there are ≥ 1 diagnoses for diabetes mellitus ICD-10 or disease codes during the baseline period.
Treated with antiplatelet drug in baseline	Baseline characteristic	Dichotomous variable equals 1 if there are ≥ 1 prescriptions of antiplatelet drug ATC or receipt codes during the baseline period.
Treated with NSAIDs in baseline	Baseline characteristic	Dichotomous variable equals 1 if there are ≥ 1 prescriptions of NSAIDs ATC or receipt codes during the baseline period.

Treated with gastric secretion inhibitor in baseline	Baseline characteristic	Dichotomous variable equals 1 if there are ≥ 1 prescriptions of gastric secretion inhibitor drug ATC or receipt codes during the baseline period.

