14 APPENDIX-3: LIST OF ANY BLEEDING

Procedure for definition of “any bleeding”

Step 1. To extract the following group A or group B from MDV data base.

Group A: ICD-10 name includes [REDACTED] (bleeding)" or [REDACTED] (ecchymoma)"

Group B: Disease name includes [REDACTED] (bleeding)" or [REDACTED] (ecchymoma)"

Step 2. To select disease names considered to be relevant to side effect of OAC individually from disease names excluded in Step 1.

Step 3. To exclude disease names which are not considered to be relevant to side effect of OAC from the disease names included in Step 1.

ICD-10	ICD10Name
A162	Tuberculosis of lung, without mention of bacteriological or histological confirmation
A165	Tuberculous pleurisy, without mention of bacteriological or histological confirmation
B303	Acute epidemic haemorrhagic conjunctivitis (enteroviral)
D500	Iron deficiency anaemia secondary to blood loss (chronic)
D62	Acute posthaemorrhagic anaemia
D66	Hereditary factor VIII deficiency
D683	Haemorrhagic disorder due to circulating anticoagulants
D698	Other specified haemorrhagic conditions
D699	Haemorrhagic condition, unspecified
E078	Other specified disorders of thyroid
E274	Other and unspecified adrenocortical insufficiency
G361	Acute and subacute haemorrhagic leukoencephalitis [Hurst]
G951	Vascular myopathies
G968	Other specified disorders of central nervous system
H052	Exophthalmic conditions
H113	Conjunctival haemorrhage
H168	Other keratitis
H208	Other iridocyclitis
H210	Hyphaema
H313	Choroidal haemorrhage and rupture
H350	Background retinopathy and retinal vascular changes
H356	Retinal haemorrhage
H357	Separation of retinal layers
H405	Glaucoma secondary to other eye disorders
H431	Vitreous haemorrhage

ICD-10	ICD10Name
H448	Other disorders of globe
H470	Disorders of optic nerve, not elsewhere classified
H603	Other infective otitis externa
H669	Otitis media, unspecified
H738	Other specified disorders of tympanic membrane
H922	Otorrhagia
I213	Acute transmural myocardial infarction of unspecified site
I230	Haemopericardium as current complication following acute myocardial infarction
I312	Haemopericardium, not elsewhere classified
I600	Subarachnoid haemorrhage from carotid siphon and bifurcation
I601	Subarachnoid haemorrhage from middle cerebral artery
I602	Subarachnoid haemorrhage from anterior communicating artery
I603	Subarachnoid haemorrhage from posterior communicating artery
I604	Subarachnoid haemorrhage from basilar artery

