K625	Haemorrhage of anus and rectum
K661	Haemoperitoneum
K762	Central haemorrhagic necrosis of liver
K768	Other specified diseases of liver
K85	Acute pancreatitis
K920	Haematemesis
K921	Melaena
K922	Gastrointestinal haemorrhage, unspecified
L508	Other urticaria
M250	Haemarthrosis
N029	Recurrent and persistent haematuria, Unspecified
N288	Other specified disorders of kidney and ureter
N300	Acute cystitis
N304	Irradiation cystitis
N309	Cystitis, unspecified
N328	Other specified disorders of bladder

ICD-10	ICD10Name
N368	Other specified disorders of urethra
N421	Congestion and haemorrhage of prostate
N488	Other specified disorders of penis
N501	Vascular disorders of male genital organs
N645	Other signs and symptoms in breast
N830	Follicular cyst of ovary
N831	Corpus luteum cyst
N836	Haematosalpinx
N837	Haematoma of broad ligament
N838	Other noninflammatory disorders of ovary, fallopian tube and broad ligament
N898	Other specified noninflammatory disorders of vagina
N908	Other specified noninflammatory disorders of vulva and perineum
N921	Excessive and frequent menstruation with irregular cycle
N922	Excessive menstruation at puberty
N923	Ovulation bleeding
N924	Excessive bleeding in the premenopausal period
N930	Postcoital and contact bleeding
N938	Other specified abnormal uterine and vaginal bleeding
N939	Abnormal uterine and vaginal bleeding, unspecified
N950	Postmenopausal bleeding
O208	Other haemorrhage in early pregnancy
O209	Haemorrhage in early pregnancy, unspecified
O441	Placenta praevia with haemorrhage
O469	Antepartum haemorrhage, unspecified
O679	Intrapartum haemorrhage, unspecified
O695	Labour and delivery complicated by vascular lesion of cord
O717	Obstetric haematoma of pelvis
O720	Third-stage haemorrhage
O721	Other immediate postpartum haemorrhage
O722	Delayed and secondary postpartum haemorrhage
O901	Disruption of perineal obstetric wound
O902	Haematoma of obstetric wound
P021	Fetus and newborn affected by other forms of placental separation and haemorrhage
P100	Subdural haemorrhage due to birth injury
P101	Cerebral haemorrhage due to birth injury
P102	Intraventricular haemorrhage due to birth injury
P103	Subarachnoid haemorrhage due to birth injury
P109	Unspecified intracranial laceration and haemorrhage due to birth injury
P120	Cephalhaematoma due to birth injury
P269	Unspecified pulmonary haemorrhage originating in the perinatal period

ICD-10	ICD10Name
P510	Massive umbilical haemorrhage of newborn

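### Any bleeding, any GI bleeding and any intracranial hemorrhage need not be new diagnoses, so old bleeds can count as events: rates are overstated and the hazard ratio can be biased

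*SAP*

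**What the plan says.** SAP 8.2 gives the rule for the any-bleeding endpoint: "Any bleeding after index date will be identified using hospital claims which had a bleeding diagnosis code". The sentence goes on to require that the code be the first one listed. Time to event runs from the index date to the first such event. The rows for any GI bleeding and any intracranial hemorrhage are built the same way. Major bleeding, by contrast, must also sit in DPC field 21, the diagnosis behind the hospitalization, and stroke/SE must sit in one of five named DPC fields.

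Protocol 7.3, Table 1 is looser. It asks only for one or more "diagnoses for any bleeding ICD-10 or disease codes during the follow-up period".

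Patients who bled before the index date are kept. SAP 8.4 records them with a yes/no flag based on "diagnoses for bleeding ICD-10 or disease codes during the baseline period", and SAP 10.1.1 puts that flag in the propensity score. Baseline bleeding is not among the listed exclusions.

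Appendix-3 lists D500, "Iron deficiency anaemia secondary to blood loss (chronic)", and N029, "Recurrent and persistent haematuria, Unspecified". It also lists I690 and I691 (sequelae of subarachnoid and intracerebral haemorrhage) and T905 (sequelae of intracranial injury). I690 and I691 appear again under intracranial bleeding in Appendix-5.

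The rank of any bleeding is not consistent. It is one of three null hypotheses in SAP 6.1 and is marked as primary for safety in both tables of SAP 10.1.8, but SAP 8.2 labels it a secondary endpoint.

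**The concern.** One continuing diagnosis can be scored twice: as baseline bleeding and then, at the first post-index visit where it is listed first, as an outcome. The database covers outpatient as well as inpatient claims (Protocol 7.2 and 7.4), and the any-bleeding rule has no admission filter, so a routine follow-up visit qualifies. Sequelae codes are the clearest case, because they describe the residue of a past bleed.

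Two planned outputs are exposed. The rate per 100 patient-years gains false events and loses the person-time that would have followed them. The hazard ratio gains events that have nothing to do with the drug started on the index date.

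**Working it through.** **What the documents supply.** The only planning figures are for another endpoint: in SAP 6.2, "the required sample size to detect a significant difference in stroke/SE was calculated". That table can be reproduced. For HR 0.6 and 1.2 %/year, the events needed are 4(1.960 + 0.842)² / ln(0.6)² = 120.3. Assuming two years of follow-up without dropout, the event probabilities are 1 − exp(−0.024) = 0.02371 and 1 − exp(−0.0144) = 0.01430. Then 120.3 / (0.02371 + 0.01430) = 3,165.3, which rounds up to the stated 3,166. The other 11 cells agree within about 1.2%. The table has no row for bleeding, so it says nothing about how large this problem is. Every bleeding rate and carry-over share below is an assumption.

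**Model.** True bleeds occur at a constant rate λ in the warfarin arm and 0.80λ in the NOAC arm. A fraction c of each arm has a carried-over code at a uniformly distributed time in days 0–60. Censoring is exponential with mean one year, capped at two years. In the first 60 days the counted hazard is λ + (c/60)/(1 − c·t/60), with t in days and λ per day; after that it is λ. I solved the large-sample Cox score equation numerically.

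Equal carry-over in both arms, true HR 0.80:

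| True warfarin rate per 100 PY | c | Warfarin rate as counted | Share of warfarin events that are false | HR as counted |
|---|---|---|---|---|
| 5 | 1% | 6.1 | 18% | 0.836 |
| 5 | 2% | 7.2 | 31% | 0.862 |
| 5 | 5% | 10.8 | 54% | 0.907 |
| 10 | 1% | 11.1 | 10% | 0.820 |
| 10 | 2% | 12.3 | 19% | 0.837 |
| 10 | 5% | 15.9 | 37% | 0.874 |

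A simple formula gives nearly the same answer. If f is the false share of warfarin events and both arms carry the same number, HR counted ≈ HR true × (1 − f) + f. With f = 0.31 this is 0.80 × 0.69 + 0.31 = 0.862.

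**Unequal carry-over.** Same model, 5 per 100 PY, warfarin carry-over fixed at 2%:

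| NOAC carry-over | 1.0% | 1.4% | 1.6% | 2.0% | 2.5% | 3.0% |
|---|---|---|---|---|---|---|
| HR as counted | 0.71 | 0.77 | 0.80 | 0.86 | 0.94 | 1.02 |

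The bias disappears when the NOAC-to-warfarin carry-over ratio equals the true HR (1.6/2.0 = 0.80). Below that ratio the estimate moves away from 1. Above it the estimate rises, and it can cross 1. If the true HR is 1 and carry-over is equal, the HR is unaffected and only the rates are wrong.

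**Power, equal carry-over.** Take a comparison with 80% power on true events at HR 0.80. It needs 31.4 / ln(0.8)² = 631 events, of which 631/1.8 ≈ 351 are in the warfarin arm. With f = 20%, each arm gains 351 × 0.2/0.8 ≈ 88 false events, giving about 806 in total at a counted HR of 0.84. Power is Φ(√806/2 × |ln 0.84| − 1.96) ≈ 70%. At f = 5, 10 and 30% it is about 78, 75 and 63%.

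**The case against.** The SAP does not count every claim that carries a bleeding code. A reader might infer that from SAP 8.2, but the code must be first listed, so an old bleed entered second on an atrial fibrillation visit does not count. That narrows the route and stands as a limit on the size of the problem. It does not make a diagnosis new: a patient seen for persistent haematuria can have it listed first both before and after the index date.

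Appendix-3 also works on disease names, and its Step 3 drops names judged irrelevant to anticoagulant side effects. The printed ICD-10 titles therefore do not show exactly which names count. This weakens the case for D500 and N029. It does little for I690 and I691, which are repeated as intracranial bleeding in Appendix-5.

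The exclusion for contraindicated use might remove some active bleeders, but the available text gives no operational rule. Protocol 7.9 acknowledges misclassification of claims diagnoses in general, without addressing diagnoses carried over from baseline. Some planned analyses are redacted, so whether a suitable sensitivity analysis already exists cannot be judged.

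Propensity matching does not remove the problem. It balances one yes/no flag, and balanced false events are still false events.

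**Conclusion.** The gap is real and worth correcting before the analysis. As written, the three any-bleeding endpoints can count a visit for an old bleed as a new event, and their rates per 100 patient-years are overstated to whatever extent that happens. This conclusion does not depend on balance between the arms.

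A reader might go further and infer that the hazard ratio is necessarily pulled toward 1. The documents do not support that. It requires roughly equal carry-over and a true HR different from 1. Baseline bleeding in the propensity score makes near-equality plausible, but the flag does not match on type or recency of bleeding, so the shift could go either way.

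The size is unknown. An HR moving from 0.80 to about 0.84–0.86 rests on an assumed 1–2% carry-over in each arm at 5 per 100 patient-years. A figure near 0.91 would need more than half of the warfarin events to be false, and nothing in the documents points to that.

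Nor should any bleeding simply be called a primary endpoint. SAP 6.1 and 10.1.8 treat it as a main result and SAP 8.2 does not, and the sponsor should reconcile these sections.

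**What to change.** 1. Remove I690, I691 and T905 from the outcome lists (Appendix-3, and Appendix-5 where they appear). Keep them in the definition of the baseline bleeding covariate.
2. For any bleeding, any GI bleeding and any intracranial hemorrhage, pre-specify an analysis restricted to patients with no bleeding diagnosis in the 180-day baseline or on the index date. Re-estimate the propensity scores and redo the matching within that subset, and report the result beside the main one.
3. If the dataset holds a diagnosis start date, count only diagnoses that start after the index date. The documents do not show whether this field exists, so steps 1 and 2 should not depend on it.

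A rule that discards any post-index code sharing a three-character ICD-10 category with a baseline code would be a poor substitute. It would still count I61 followed by I691, or K254 followed by K922 or D500, and it would drop true re-bleeds.

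The cost is SAP wording, some programming and one additional set of matched analyses, with no new data collection. The restricted analysis has fewer patients and does not cover re-bleeding after a recent bleed, which the main analysis still shows.
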